9.3.11 Quality of Life: EQ-5D-5L Health Questionnaire

The EuroQoL 5 Dimensions 5 Levels (EQ-5D-5L) questionnaire is assessed monthly through Month 12; all data will be listed.

The EQ-5D-5L health questionnaire consists of five-dimension scores for mobility, self-care, usual activities, pain/discomfort, and anxiety/depression. Each dimension score has values of 1-5 with a higher number representing worse quality of life. Refer to protocol Appendix 5 for more details. Each EQ-5D-5L domain score will be summarized as a categorical variable by treatment for each visit.

The EQ-5D-5L health profile, defined by the EQ-5D-5L descriptive system, may be converted into a single index score on the basis of the US set of weights using the EuroQol value level dataset which contains the values of the EQ-5D-5L crosswalk index values (19). The US EQ-5D-5L index score is a numeric value in the range of -0.109 to 1.00 with a higher number generally representing a better quality of life. The EQ-5D-5L index score will be summarized as a continuous variable. The index score and change from baseline will be summarized by treatment for each visit. In addition, the change from baseline will be compared at visits with data collected for both treatment groups using the same method as that for CLIF-C OF scores.

GRIFOLS	Bioscience Industrial Group	Number	IG1601	Statistical Analysis Plan
		Version	2.0	Page
09-Sep-2024	40 of 52	Effective Date	Effective	

The EQ-5D-5L Visual Analog Scale (EQ VAS) rates the subject's health on a scale of 0 to 100, with a higher number representing better health. The EQ VAS score will be summarized as a continuous variable. The VAS score and change from baseline will be summarized by treatment for each scheduled visit. In addition, the change from baseline will be compared for scheduled visits with data collected for both treatment groups in the same way as CLIF-C OF scores.

10 Safety Analysis

Unless otherwise noted, all Safety listings and summaries will be based on the Safety population.

10.1 Adverse Events

Adverse Events are coded using the MedDRA coding dictionary (a version within 1 year of the data base lock). A treatment emergent adverse event (TEAE) is defined in [Section 6.1.6](#). A suspected ADR is an adverse event with causal relationship of "definitely related" or "possibly related", as classified by the investigator. An adverse reaction (AR) is an adverse event with causal relationship of "definitely related", as classified by the investigator.

A temporally associated (i.e., infusional) AE is an AE that is temporally associated with the infusion of Albutein 20%, and is identified as an AE that occurs during an Albutein infusion (as recorded by the investigator), or within 72 hours following an Albutein infusion (determined by calculating the time from infusion end to AE start). These definitions only apply to subjects in the SMT + Albutein 20% group.

All adverse events, both treatment-emergent and non-treatment emergent, will be included in a listing, with a flag to distinguish whether or not the event is treatment-emergent.

An overall summary of TEAEs will present the number of TEAEs, and the number and percentage of subjects with TEAEs, in the following categories:

- AE with Onset Prior to Treatment
- TEAE
- Suspected ADR
- AR
- TEAE Leading to Death
- Serious TEAE
- Serious Suspected ADR
- Serious AR
- Non-Serious TEAE
- TEAE Leading to Drug Interruption
- TEAE Leading to Drug Withdrawal
- TEAE Leading to Study Withdrawal

GRIFOLS	Number	IG1601	Big-CL-SP-000319
	Version	2.0	Statistical Analysis Plan
	Effective	Effective Date	09-Sep-2024
	Page		41 of 52

- Temporally associated TEAEs

In addition, TEAEs will be summarized in the following ways:

- SOC / PT – summary of number of TEAEs and number/percentage of subjects with at least one TEAE by treatment, SOC and preferred term
 - A select subset of TEAE summaries will also include number of events by SOC and preferred term
- PT – summary of number of TEAEs and number/percentage of subjects with at least one TEAE by treatment and preferred term
- SOC/PT/Severity – summary of number of TEAEs and number/percentage of subjects with at least one TEAE by treatment, SOC, preferred term, and severity
- SOC / PT / Causality – summary of number of TEAEs and number/percentage of subjects with at least one TEAE by treatment, SOC, preferred term, and causality
- PT Rates – summary of number of infusions, number of adverse events, rate of adverse events per infusion, and rate of adverse events per exposure week by preferred term. Rate per infusion is defined as total number of events divided by total number of infusions received. Rate per exposure week is defined as total number of events divided by total duration of exposure in weeks. This summary applies to the SMT + Albutein 20% group only

At each level of summarization, a subject will only be counted once per SOC or preferred term, using the most severe AE or the AE with the strongest causal relationship to the treatment as applicable. Summary tables will be sorted in descending frequency within the SMT + Albutein 20% group, then descending frequency with the SMT group, and then alphabetically.

The following table identifies the sets of adverse events that will be presented for each of these types of summaries.

Adverse Event Subset	TEAE Summary					Listing
	SOC / PT	PT	SOC / PT / Severity	SOC / PT / Causality	PT Rates*	
AE with Onset Prior to Treatment						
TEAEs						
Suspected ADR						
AR						
TE SAEs						
Non-serious TEAEs	 #					
TEAEs leading to Study Withdrawal						
TEAEs leading to Death						
Temporally associated TEAEs*						

* This subset applies only to the SMT + Albutein 20% group.

This summary will include number of events by SOC / PT.

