5.3.2 Discontinuation of Subjects from Treatment

If a subject receives a liver transplant, study treatment and all treatment-related assessments will be discontinued upon transplant. The criteria to determine when a subject becomes a candidate for liver transplantation is described in Section 5.3.2.1. The subject will continue to have subsequent planned visit assessment procedures performed.

Discontinuation of the treatment in subjects who receive a TIPS insertion will be at the discretion of the investigators. In case it is decided to discontinue the subject's treatment early, study treatment will be stopped and the subject will continue to have subsequent planned visit assessment procedures performed.

Adverse events that will determine temporary subject's discontinuation from study treatment include the following:

• Subjects developing severe bleeding, Albutein 20% infusions will be temporarily stopped until the bleeding episode is resolved. For subjects with variceal bleeding, Albutein 20% infusions will be temporarily stopped until the subject has received at least 2 banding sessions. Albutein 20% infusions will be resumed after the bleeding episode is resolved or after the subject has received at least 2 banding sessions, respectively.

Adverse events that will determine permanent subject's discontinuation from study treatment include the following:

- Anaphylactic shock or transfusion-related acute lung injury
- Severe AEs (ie, acute myocardial infarction, cerebral hemorrhage, cardiac failure, pulmonary edema, or intestinal necrosis) that precludes the continuation of the subject in the clinical study

Subjects with any one of these severe AEs will be discontinued from study treatment and all treatment-related assessments, and should continue to have subsequent planned visit assessment procedures performed.

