8.2.1 Adverse Events

Adverse events (includes suspected ADRs) occurring at any time between signing of the subject's ICF and the last day of the subject's participation (End of Study or Early Discontinuation Visit) in the clinical study will be reported and recorded on the appropriate subject's eCRF entry and subject's source documents.

It is the investigator's responsibility to ensure that all AEs including suspected ADRs are appropriately recorded.

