9.1.3.1 Adverse Events

Adverse events will be coded and classified using MedDRA[®] terms (system organ class and preferred terms).

When a causal relationship of an AE is classified by the investigator as definitively or possibly related, the event will be defined as a suspected ADR. A suspected ADR with a causal relationship of "definitively related" will be defined as an AR. The sponsor will consider the investigator's causality assessment and also provide its own assessment. If there is any disagreement in the causality assessment between the investigator and the sponsor, a separate summary of suspected ADRs/ARs will be provided.

For summary purpose, AEs will be classified as treatment-emergent AEs (TEAEs) or non-TEAEs depending on the comparison of AE onset date/time with the start date/time of study treatment. A TEAE will be defined as an AE which occurs between the start of study treatment and the final visit of the clinical study. A non-TEAE will be defined as an AE which occurs prior to the start of study treatment. Non-TEAEs and TEAEs will be summarized separately.

In addition, TEAEs, including suspected ADRs, will be summarized by each treatment group, system organ class, preferred term, causal relationship, severity, and seriousness (serious versus non-serious) using descriptive statistics. At each level of summarization, a subject will only be counted once per system organ class or preferred term using the most severe AE or the AE with the strongest causal relationship to the treatment.

AEs temporally associated with the infusion of the IP (ie, infusional AEs, including infusional suspected ADRs) will be summarized by presenting infusion/subject incidences and percentages and listed.

Subjects with SAEs, AEs leading to death, or who withdraw from the study because of an AE will also be individually listed and summarized.

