6.1.6 Adverse Events

Adverse events will be classified as TEAEs or non-Treatment-Emergent AEs (non-TEAEs), based on the comparison of the AE onset date/time with the start date/time of study treatment. For the SMT + Albutein 20% treatment group, TEAE is defined as an AE occurring during or after the first Albutein dose administration. For the SMT treatment group, it is assumed that subjects were already receiving SMT per institutional standards at the time of randomization; therefore, a TEAE will be defined as an AE occurring at or after randomization.

A non-TEAE will be defined as an AE which starts during screening and prior to the start of the first administration of study treatment in the SMT + Albutein 20% treatment group. For the SMT group, a non-TEAE is an AE that starts during screening and prior to randomization.

An AE with incomplete start date/time will be determined to be a TEAE or non-TEAE using the conservative rule specified in [Appendix 2](#).

Any AE with a missing end date will be considered ongoing.

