8.3 Extent of Exposure to Albutein 20%

For subjects randomized to SMT + Albutein 20%, all Albutein exposure details will be listed by visit.

An overall summary of exposure will present the duration of exposure (weeks), number of infusions received, number of subjects who had 4 or more missing consecutive infusions, and the total volume infused (mL). Duration of exposure is defined as [(date of last infusion – date of first infusion) + 10]/7. Interruptions, dose changes, and compliance are not considered in the calculation of duration of exposure.

Albutein infusion interruptions will be summarized by visit. Number of infusions, number and percentage of infusions with interruptions, and number and percentage of infusions with interruptions due to TEAE will be summarized.

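### The Albutein TEAE rate per exposure week counts events up to the final visit but divides by time that ends 10 days after the last infusion, so subjects who stop infusions and stay in the study bias it upward.

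*SAP*

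**What the plan says.** **The rate.** SAP 10.1 plans a preferred-term rate table for the SMT + Albutein 20% group only. It has rows for TEAEs, suspected ADRs, ARs and temporally associated TEAEs. "Rate per exposure week is defined as total number of events divided by total duration of exposure in weeks".

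**The denominator.** SAP 8.3: "Duration of exposure is defined as [(date of last infusion – date of first infusion) + 10]/7". It adds: "Interruptions, dose changes, and compliance are not considered in the calculation of duration of exposure". A temporary gap therefore stays in the exposure time; only time later than 10 days after the last infusion is left out.

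**The numerator.** For the Albutein arm, SAP 6.1.6 says: "TEAE is defined as an AE occurring during or after the first Albutein dose administration". It sets a start and no end. Protocol 9.1.3.1 supplies one: "A TEAE will be defined as an AE which occurs between the start of study treatment and the final visit of the clinical study". Protocol 8.2.1 and 8.3.8 likewise collect adverse events up to the End of Study or Early Discontinuation Visit.

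**Who can stop infusions and stay.** Under protocol 5.3.2, "study treatment and all treatment-related assessments will be discontinued upon transplant", yet the subject's later planned visits go ahead. The same holds after the listed severe adverse events, and after TIPS if the investigator decides to stop infusions. Adverse-event recording is part of those visits (protocol 7.2.1.2).

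**The concern.** The two halves of the rate cover different periods. Once a subject is more than 10 days past the last infusion and still attending visits, each new TEAE enters the numerator while the weeks in which it arose are absent from the denominator. The result is neither an on-treatment rate (events and time both limited to exposure) nor an on-study rate (both running to the final visit).

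The group affected is part of the design. Transplant is a component of the primary endpoint, and SAP 10.1 itself lists events leading to drug withdrawal separately from those leading to study withdrawal. PT Rates is also the only adverse-event summary in SAP 10.1 that divides events by time or by infusions. A reader of the study report would take the figure as the event rate during Albutein exposure, and it would be too high for that.

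**Working it through.** **Inputs from the documents.** Infusions are every 10 days and the Month 12 visit is Day 361 (protocol 7.2.1.2). Completers return within one week, so to Day 368 at the latest (protocol 7.2.1.3). Exposure is as defined in SAP 8.3.

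**The plan's own figure.** SAP 8.4 expects 37 infusions for a completer: (361 − 1)/10 + 1 = 37. It reproduces. The documents state no event rate, event count or total exposure.

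**Completers.** Exposure = (360 + 10)/7 = 52.86 weeks. Event collection to Day 368 = 368/7 = 52.57 weeks. The ratio is 52.57/52.86 = 0.99, so there is no inflation.

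**One subject who stops but is followed to Day 361.** Exposure for a last infusion on Day L is [(L − 1) + 10]/7, against 361/7 = 51.57 weeks of collection. With a constant event rate:

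| Last infusion | Exposure (weeks) | Collected/exposure |
|---|---|---|
| Day 61 | 10.00 | 5.16 |
| Day 91 | 14.29 | 3.61 |
| Day 181 | 27.14 | 1.90 |
| Day 271 | 40.00 | 1.29 |
| Day 351 | 51.43 | 1.00 |

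**Pooled arm.** The SAP pools events and exposure over subjects. Assume that a share f stops s weeks after the first infusion and stays to Day 361, that everyone else completes, and that the event rate is constant. Each stopper is credited E = s + 10/7 weeks. Then

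inflation = [(1 − f) × 52.57 + f × 51.57] / [(1 − f) × 52.86 + f × E].

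| f | s | E | Numerator | Denominator | Inflation |
|---|---|---|---|---|---|
| 10% | 26 | 27.43 | 52.47 | 50.31 | 1.04 |
| 20% | 13 | 14.43 | 52.37 | 45.17 | 1.16 |
| 30% | 8.7 | 10.13 | 52.27 | 40.04 | 1.31 |

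**If the rate differs off treatment.** Let k be the event rate after credited exposure ends, relative to the rate before. Replace 51.57 in the numerator by E + k × (51.57 − E). For f = 20%, s = 13, the unmatched time is 51.57 − 14.43 = 37.14 weeks, and 0.8 × 52.57 = 42.06:

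- k = 0: (42.06 + 0.2 × 14.43)/45.17 = 0.99, so no inflation
- k = 0.5: (42.06 + 0.2 × 33.00)/45.17 = 1.08
- k = 2: (42.06 + 0.2 × 88.71)/45.17 = 1.32

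For f = 10%, s = 26 (for example, transplants at mid-year), the unmatched time is 24.14 weeks and 0.9 × 52.57 = 47.31. Then k = 2 gives (47.31 + 0.1 × 75.71)/50.31 = 1.09, and k = 3 gives (47.31 + 0.1 × 99.86)/50.31 = 1.14.

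The values of f, s and k are all assumptions.

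**Rows of the table.** Temporally associated events occur during an infusion or within 72 hours after it (SAP 10.1), inside the 10 days, so that row is matched. Suspected ADRs and ARs require a causal attribution to Albutein, so a late event reaches those rows only if so attributed. The TEAE row takes all late events.

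**The case against.** The strongest reply is that the group concerned is narrow and the table has little weight. Much of this stands.

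- **Dropouts are largely unaffected.** Event collection ends at the Early Discontinuation Visit, preferably within a week of withdrawal (protocol 5.3.5), and later contacts record only transplant, survival and cause of death. A reader might take the planned 20% dropout rate as the share that stops but stays. The documents do not support that; they give no frequency for the protocol 5.3.2 group.
- **Not every stop matters.** A reader might infer that any early stop inflates the rate, or that exposure ends at the last infusion itself. Neither is so: SAP 8.3 adds a full dosing interval and keeps temporary gaps. For a subject who dies or leaves within 10 days of the last infusion, the formula credits slightly more time than was observed.
- **Disease progression is mostly excluded.** Protocol 8.3.10 generally does not count anticipated progression as an adverse event, which limits the late events that can enter.
- **No comparison is damaged.** The table is single-arm by design. Between-arm safety review rests on counts and subject percentages, which are unaffected. The bias is upward, so it would not conceal harm.
- **No subgroup rate is planned.** A reader might say that the bias is worst for subjects who stopped because of harm or transplant. They are its source, but the SAP reports only a pooled rate.

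One could also argue that treatment-related assessments, which protocol 5.3.2 ends at transplant, include adverse-event recording. The protocol does not say so, and 8.2.1 ties collection to the last day of participation.

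None of this supplies the missing end to the event window for the TEAE row.

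**Conclusion.** The mismatch is in the text, and its direction is upward for the TEAE row. Suspected ADR and AR rows are affected only through late events attributed to Albutein; the temporally associated row is not affected.

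The size cannot be derived from the documents. In the illustrative cases it runs from about 1.04- to 1.31-fold. Those figures rest on an assumed share of subjects who stop but stay, an assumed stopping time, a constant event rate, follow-up of stoppers to Day 361, and completion by everyone else. The last two are simplifications, since the plan itself assumes 31% transplant or death in this arm by one year. The inflation disappears if no events occur off treatment and grows if they become more frequent there.

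A reader might extend the criticism to the rate per infusion, whose numerator is equally open-ended. That rate is explicitly defined as events over infusions received and does not claim to be a rate over time. Restricting it to temporally associated events would be a preference, not a correction.

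This is a minor correction to a descriptive safety table. No hypothesis test, efficacy result or between-arm comparison changes.

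**What to change.** In SAP 10.1, give the rate per exposure week one stated window, by either route:

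1. **On-treatment rate:** count only events with onset from the first infusion to 10 days after the last infusion, and keep the SAP 8.3 denominator.
2. **On-study rate:** keep all TEAEs, and divide by weeks from the first infusion to the subject's final adverse-event collection visit.

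Label the table with the one reported. Either is sufficient.

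The cost is a sentence of SAP wording and one derived variable. The dates needed (infusions, event onset, final visit) are already collected; SAP 8.4 already uses the end-of-study visit date.

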9.1.3 Safety Analysis

The safety analyses will be addressed by listing and tabulation of AEs (including suspected ADRs), vital signs, physical assessments, and clinical laboratory tests. Data will be described using descriptive analyses and treatment comparisons will be based on review of descriptive statistics. The safety analyses will be based on the Safety population.

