6.2 Sample Size

Based on the CANONIC study, the overall 1-year transplant-free mortality rate in the current study population is assumed to be about 46% (11,16). Assuming a potential drop-out rate of 20% and 5% type-1 error for a 2-sided Chi-square test, a global sample size of 410 patients (205 per treatment group) will allow an 80% statistical power to detect an absolute reduction of 15% (17) for the 1-year mortality rate in subjects treated with SMT + Albutein 20%.

GRIFOLS	Number	IG1601	Version	2.0	Status	Effective	Effective Date	09-Sep-2024	Page	22 of 52
BIG-CL-SP-000319 IG1601 Statistical Analysis Plan										

GRIFOLS	Number	BIG-CL-SP-000319		Version	2.0	Status	Effective	Effective Date	09-Sep-2024	Page	23 of 52
	IG1601 Statistical Analysis Plan										

Alternatively, the sample size was calculated based on the log-rank test as follows. Assuming the 1-year transplant or mortality rate is 46% for the control group, or equivalently, the transplant-free survival rate is 54%, which translates to a hazard rate of 0.0017 assuming an exponential distribution. Using a log-rank test at the 2-sided significant level of 5%, a total of 125 events would provide at least 80% power to detect an absolute reduction of 15% in transplant or mortality rate (a 31% 1-year transplant or mortality rate, or equivalently, a 69% transplant-free survival rate) in subjects treated with SMT + Albutein 20%. This absolute difference in transplant or mortality rates translates to a hazard ratio of 0.6022, or an approximate 40% risk reduction. With all subjects followed for the entire 1-year duration of the study, a total of 322 subjects would be required to obtain 125 events. Assuming a dropout rate of 20%, a global sample size of 404 subjects (202 per treatment group) is required. This sample size calculation was performed using Proc Power with the two-sample survival statement in SAS version 9.4.

Taking a conservative approach, the larger of the 2 sample sizes (i.e., 410 subjects based on the Chi-square test) will be used to ensure the study has sufficient power.

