6.3 Randomization and Blinding

This is an open-label study. Subjects will be randomized into one of two groups (SMT + Albutein 20% versus SMT alone) in a 1:1 ratio based on a computer-generated randomization schedule. Randomization of subjects will be stratified by region (Europe or North America) and by whether or not subjects have been previously hospitalized for acute decompensation of liver cirrhosis prior to the most recent hospitalization for acute decompensation of liver cirrhosis with ascites as required by Inclusion Criterion #3v4. Within each stratum (i.e., each unique combination of region and history of hospitalization for acute decompensation of liver cirrhosis), eligible subjects will be randomized in a 1:1 ratio into 1 of 2 treatment groups.

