6.5 Hypothesis Testing and Multiplicity Adjustments

All statistical tests will be 2-sided with significance level fixed at 0.05.

The fixed-sequence testing method will be used to adjust for multiplicity in the analyses of the secondary efficacy endpoints (using the ITT population). Specifically, the superiority of SMT + Albutein 20% versus SMT alone for the secondary efficacy endpoints will only be tested if the superiority for the primary efficacy endpoint is demonstrated at the 2-sided significance level of 5% (for ITT population).

For the secondary efficacy endpoints, each subsequent hypothesis is tested only if the superiority for the previous comparison(s) listed below has been demonstrated at a 2-sided significance level of 5%. The order in which the null hypotheses will be tested is predetermined for the secondary efficacy endpoints as follows:

1. Time to death through 1 year after randomization
2. Time to liver transplantation or death through 6 months after randomization
3. Time to death through 6 months after randomization
4. Time to liver transplantation or death through 3 months after randomization
5. Time to death through 3 months after randomization
6. Total number of paracenteses
7. Incidence of refractory ascites according to the ICA criteria

No other adjustments for multiplicity are planned. P-values will be displayed for all the above pre-specified tests for completeness; interpretation and reporting of significant hypothesis test results will follow the fixed sequence approach described.

GRIFOLS	Bioscience Industrial Group	Number	IG1601	Version	2.0	Status	Effective	Effective Date	09-Sep-2024	Page	24 of 52
		IG1601	Statistical Analysis Plan								

7 Subject Disposition and Demographics

Unless otherwise noted, all demographics listings and summaries will be based on the ITT population. Subjects who were incorrectly stratified at the time of randomization will be listed and summarized.

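### Adverse event rates per week are planned for the Albutein arm only, so the between-arm adverse event comparison rests on crude counts and percentages that depend on follow-up time

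*SAP*

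**What the plan says.** Protocol 9.1.3 makes the safety analysis descriptive: "treatment comparisons will be based on review of descriptive statistics". SAP 10.1 carries this out with by-treatment tables of the number of treatment-emergent AEs (TEAEs) and the number and percentage of subjects with at least one, overall and by system organ class, preferred term, severity and causality.

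The one AE table with a time denominator is the preferred-term rates table in SAP 10.1. It gives a rate per infusion and a rate per week: "Rate per exposure week is defined as total number of events divided by total duration of exposure in weeks". It then adds: "This summary applies to the SMT + Albutein 20% group only". SAP 8.3 derives duration of exposure from first and last infusion dates, so the SMT arm has no exposure time at all. Neither document plans a person-time rate, a time-to-first-event analysis or a cumulative-incidence analysis of AEs for SMT.

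For other counts the SAP does adjust for time in both arms. Paracenteses (SAP 9.2.6) and cirrhosis readmissions (SAP 9.3.6) are modelled by Poisson regression with log treatment duration as an offset.

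**The concern.** A per-infusion rate cannot exist for SMT, but a per-week rate can. TEAEs on SMT have a defined start, randomization (SAP 6.1.6), and AE recording has a defined end, the End of Study or Early Discontinuation Visit (Protocol 8.2.1). Without that rate, any difference in AE or serious AE counts mixes a difference in risk with a difference in time observed.

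The trial is designed to produce a difference in time observed. If Albutein prolongs survival, its subjects have longer to accrue AEs, and equal risk shows as an excess on Albutein. If more Albutein subjects leave the study, the distortion runs the other way. A reader of the planned tables could not tell which applies.

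**Working it through.** **Inputs.** Control 1-year event rate 46% (SAP 6.2: "Assuming the 1-year transplant or mortality rate is 46% for the control group"). Albutein rate 31% (SAP 6.2: "a 31% 1-year transplant or mortality rate, or equivalently, a 69% transplant-free survival rate"). Dropout 20% (SAP 6.2). Allocation 1:1 (SAP 6.3: "eligible subjects will be randomized in a 1:1 ratio into 1 of 2 treatment groups"). Two-sided 5% level (SAP 6.5: "All statistical tests will be 2-sided with significance level fixed at 0.05"). Exponential event times, as in SAP 6.2.

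**Reproducing the plan's own figures.**
- Yearly hazards: SMT −ln(0.54) = 0.6162; Albutein −ln(0.69) = 0.3711. Daily on SMT: 0.6162/365 = 0.0017, as stated.
- Hazard ratio: 0.3711/0.6162 = 0.6022. The plan says that the difference "translates to a hazard ratio of 0.6022, or an approximate 40% risk reduction".
- Events for 80% power: 123 (Schoenfeld) or 128 (Freedman), against 125 stated. Power with 125 events: 80.9%.
- Chi-square sample size: 165 per arm, and 165/0.8 gives 207 per arm, 413 to 414 in total, against 410 stated (within 1%).

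The design assumptions are therefore read correctly.

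**Mean time under AE observation.** Up to 1 year, with total hazard h for leaving observation, mean time is (1 − e^(−h))/h years. What ends AE observation matters. After a transplant, study treatment stops but planned visits continue (Protocol 5.3.2), so only death or leaving the study ends it. The documents do not give the share s of composite events that are deaths, so it is varied and taken as equal in both arms. Deaths after transplant are not modelled separately. Dropout of 20% is a hazard of −ln(0.80) = 0.2231. So h = s × event hazard + 0.2231.

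| Assumed death share s | h, SMT | h, Albutein | Mean years, SMT | Mean years, Albutein | Ratio |
|---|---|---|---|---|---|
| 50% | 0.531 | 0.409 | 0.776 | 0.821 | 1.06 |
| 70% | 0.654 | 0.483 | 0.734 | 0.793 | 1.08 |
| 85% | 0.747 | 0.539 | 0.704 | 0.773 | 1.10 |
| 100% | 0.839 | 0.594 | 0.677 | 0.754 | 1.11 |

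With equal true AE rates, expected counts are proportional to mean time, so Albutein would show about 6% to 11% more events. In the last row, 205 subjects per arm give 139 and 155 person-years. A rate per patient-week would return a ratio of 1.00 in every row.

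**Subjects with at least one event.** With an AE rate of r per year, equal in both arms (assumed), the expected proportion is r/(r + h) × (1 − e^(−(r + h))). For s = 100%, the most unfavourable row:

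| AE rate per year (assumed) | SMT | Albutein | Gap, points |
|---|---|---|---|
| 0.25 | 15.2% | 16.9% | 1.7 |
| 1 | 45.7% | 50.0% | 4.3 |
| 3 | 76.5% | 81.2% | 4.7 |
| 10 | 92.3% | 94.4% | 2.1 |

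Over all values of r the gap peaks at about 5 points, near r = 2.

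**Other directions.** With no survival benefit and equal dropout, h is the same in both arms and the ratio is 1.00. With the full benefit, 20% dropout on SMT and 40% on Albutein, the ratio is 0.98 for s = 100%, 0.95 for s = 70% and 0.93 for s = 50%.

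**Scheduled visits at which AEs are recorded from Day 1** (Protocol 7.2.1.2 and 7.2.1.3). Both arms: Day 1, Day 11, Months 1 to 11, Month 12, End of Study = 1 + 1 + 11 + 1 + 1 = 15. Albutein also has 23 treatment-only days, giving 38.

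**The case against.** The plan has real points in its favour.

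- **The main safety variable exists in one arm only.** It is suspected adverse drug reactions, which SAP 5.4.2 declares not applicable to SMT. The SAP gives time-adjusted rates where that variable exists. This stands, but overall TEAEs and serious AEs are also named safety variables and are tabulated for both arms.
- **The gravest outcomes are handled with time.** Death is compared by stratified Cox and log-rank methods (SAP 9.2.1), and cirrhosis readmissions by an offset model (SAP 9.3.6). Anticipated disease progression, and deaths unequivocally due to it, are kept out of the AE and serious AE reports (Protocol 8.3.3.1, 8.3.10 and 8.3.11.2). A reader might infer that the safety objective has no time-adjusted comparison of any kind. That goes too far: the gap is in the AE tables.
- **The size is modest.** A reader might take about 12% as the expected excess, from 0.835/0.747 = 1.12 with no dropout and all composite events ending observation. The documents do not support that as the expected value. Visits continue after transplant, and the plan itself assumes 20% dropout.
- **Hidden harm is not the likely result.** A reader might infer that crude tables would conceal a real excess on Albutein. Stopping infusions does not end planned visits (Protocol 5.3.2), so only leaving the study does. It takes clearly higher study dropout on Albutein to reverse the ratio, and even 40% against 20% lowers counts by only 2% to 7%.

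None of this explains why a per-week rate should be withheld from the SMT arm.

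**Conclusion.** The point holds in limited form. The between-arm comparison of AEs and serious AEs has no time adjustment, although the SAP adjusts paracenteses and readmissions for the same reason in both arms. Under the full planned effect and 20% dropout in each arm, the distortion is about 6% to 11% in event counts and at most about 5 percentage points in subjects affected, against Albutein.

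This rests on exponential event and dropout times, on constant and equal AE rates, and on an assumed death share of 50% to 100%. It is zero without a survival benefit if dropout is equal, and it reverses modestly if study dropout is much higher on Albutein. It is a matter of interpretability, worth fixing because the fix is cheap. It is not an error in the primary analysis.

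**What to change.** In SAP 10.1, for TEAEs and serious TEAEs, add events per patient-week on study in both arms.

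- **Clock.** Start at the opening of the TEAE window in SAP 6.1.6: randomization for SMT, first infusion for Albutein, normally the same day. Stop at the last AE-collection date: final visit, death or withdrawal. Include time after transplant or after stopping treatment while AEs are still collected.
- **Denominator.** Do not reuse the infusion-based duration in SAP 8.3. It ends 10 days after the last infusion, while TEAEs go on being counted.
- **Keep** the per-infusion rates for Albutein only.
- **Footnote** that AEs are elicited at 38 scheduled visits on Albutein and 15 on SMT, including End of Study. A rate does not correct unequal ascertainment.

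The cost is one new derived time variable and a second denominator beside infusion exposure, which needs clear labelling. The rate is an average over follow-up and says nothing about timing. No visit, procedure or hypothesis test changes, and the dates needed are already collected.
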